An opportunity to increase initiation of weight loss treatment is present in the primary care encounter. Brief primary care weight counseling has been shown to increase patient motivation for weight loss. However, this rarely translates into significant weight reductions. It may be possible to achieve significant weight loss if this motivational opportunity was used to engage patients in evidence-based weight loss treatment. To do this, primary care weight counseling must address psychosocial determinants of treatment initiation. Given the limited time and other barriers to addressing these factors during the primary care appointment, it may be most effective and cost-efficient to target these factors with a web-based intervention that is completed by patients remotely, prior to their clinical visit. This intervention could target treatment initiation determinants and offer patients the opportunity to immediately enroll in weight loss treatment. For patients who are not responsive to initial intervention content (i.e., who do not immediately enroll in treatment), further content could be delivered to promote and assist patients in initiating an effective discussion about weight with their provider at their forthcoming clinical appointment. We are proposing a feasibility/acceptability pilot test of such an intervention.

4. Design & Procedures:

Design This is a parallel-arms pilot cluster randomized clinical trial. The unit of randomization is the primary care provider and the study arms are intervention and comparison. A 1:1 randomization allocation ratio will be used.

Procedures. Up to six primary care providers will be recruited (see below for details). Once consented, providers will be randomized to the intervention or comparison condition. Patients who have clinical visits (*index PCP visit*) scheduled with enrolled providers will be identified, recruited, and consented prior to their appointments (see additional details below). We will recruit up to 12 patients per provider, for up to 72 total participants (with an intent of enrolling 60 total participants). Participants will be recruited for and enrolled in the study arm that their provider was assigned to.

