
 English speaking BMI $\geq 29 \text{ kg/m}^2$ by self-report (to allow for under-reporting) Regular email usage, defined as accessing email 3 or more times per week (on home or work computer or cell phone) 	
 In weight loss treatment program in past year Unable to read content on websites without any assistance

6. Subject Recruitment & Compensation:

Provider recruitment.

Clinic leadership at several Duke PCRC clinics will be contacted to determine willingness to allow recruitment of their physicians. We will request to attend a provider meeting to describe the study and enroll eligible providers (see recruitment script). Interested providers who meet eligibility criteria (see Table 1) will be consented by PI or the project coordinator in a private room. Providers will be paid \$100 for their time at the end of the study after completing the phone interview. We will recruit up to 6 providers.

Patient recruitment.

A DEDUCE search will be used to identify potentially eligible patients. Individuals who appear eligible based on record review using DEDUCE (see Table 1 for criteria) will be emailed a recruitment letter that is signed by the patient's primary care provider. The email from the providers will be sent using the study-specific email ([contact]). The letter will include a number to call to opt-out. If individuals do not opt out within one week, we will call them to determine if they are eligible and interested (we have proposed one week, given that we will be recruiting by email and thus there is not the typical delay of a mailed letter). Participants who are eligible and interested will be consent by phone (see phone script). We will recruit up to 12 patients per provider, for a total of up to 72 patient participants (with an intent of enrolling 60 total participants).

Participants will be compensated \$15 for completing the baseline questions (on phone or in-person, depending on assignment). They will be compensated \$5 for answering the questions immediately after their medical visit, and \$40 for attending the 6 month outcome session, for a total possible compensation of \$60.

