1. If they select Track, they will be sent an email from Your Wellness Prescription that asks a few screening questions and includes a consent for the study (see the approved Track amendment and the Track consent (Qualtrics) document). For participants who consent, they will be asked to provide their phone number. Track intervention personnel will then call patient to initiate the treatment.
2. If they select Weight Watchers, they will be emailed a unique promo code, a link to a website to sign up for Weight Watchers, and instructions for how to enroll.
3. If they select Jenny Craig, they will be emailed a letter that they will be asked to bring to one of two local Jenny Craig facilities (letter provided). This will assist the

Jenny Craig staff in recognizing that they qualify for free enrollment. Study staff will receive a periodic bill for services.

10. Risk/Benefit Assessment: There are few potential risks associated with study participation. The intervention itself may result in participants feeling uncomfortable answering questions. However, they can discontinue the intervention at any time by closing their web-browser. There is the potential risk of loss of confidentiality. However, we are minimizing this risk via efforts to secure data, including keeping data stored on a secure server accessed only by authorized study staff. The primary benefit to participants is free access to weight loss programs.

11. Costs to the Subject: There will be no direct cost to subjects. If subjects decide to join a weight loss program at the end of this study, they may have to pay for the cost of the food they eat during the program.

12. Data Analysis & Statistical Considerations: Our primary outcomes are feasibility and acceptability outcomes and are mostly descriptive. Our data analyses plan is as follows:

1. **Recruitment:** Descriptive data on recruitment rate (number of eligible patients identified and proportion of eligible patients who consent), reasons for ineligibility, and reasons for declined enrollment. We will use chi-square analyses to compare recruitment of participants who are informed that a baseline study visit is required vs. participants who are no required to attend a baseline visit.

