2. **Intervention use:** We will present descriptive data on 1) the portion of participants initiating the "Your Wellness Prescription Planning Tool" intervention, 2) portion of intervention participants completing the intervention, 3) average and range of page clicks on feedback report (as an indicator of engagement). This data will be obtained
3. **Intervention acceptability and clinical visit experience.** Descriptive data on the acceptability questions and on questions about medical visit experience will be presented.
4. **Provider acceptability:** Qualitative interviews with providers will be recorded and transcribed and analyzed using direct content analyses.
5. **Study retention.** Completion rates for 6-month assessments will be presented for entire sample and will be presented by study condition and demographics (age, race/ethnicity, gender). These will be compared against the goal of 80% retention.
6. **Weight loss enrollment, sustained engagement, and weight change:** Although the study is underpowered to make conclusions on weight loss enrollment, we will present descriptive data on treatment enrollment, sustained treatment use, and weight change, including presenting it by study condition.

13. Data & Safety Monitoring: This is a minimal risk study so the potential for serious adverse events related to the study is low. The study PI ([name]) will be responsible for monitoring participant safety during the study. Study participants will be asked to contact the PI to report any concerns or adverse events. Additionally, staff will collect information on adverse events when they are volunteered by study participants, and this information will be immediately reported to [name]. (Because this is a single session intervention with only one follow-up visit, additional proactive monitoring would be burdensome to participants). All serious adverse events will be reported to the IRB according to local IRB requirements (within 5 days of event) and will be reported to NIH on the progress report. A Data Monitoring Committee will be formed consisting of the

study PI, [name] (primary care physician and obesity expert) and one additional faculty member who is independent from the study team. The team will convene yearly or more often as needed. The team will also look at data as the study progresses, including adverse events and any serious unrelated adverse events.

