The study PI, [name], will be leaving her position at Duke and beginning a position as Assistant Professor at University of Florida in January 2018. In order for her to oversee the study after she leaves Duke, as well as to be able to analyze the data from this study for purpose of publication, she is requesting a transfer of data including PHI to University of Florida.

14. Privacy, Data Storage & Confidentiality – Paper documents that will be collected will be the payment form, which includes SSN, and patient assessment forms. This will be kept in a locked filing cabinet belonging to the PI or Co-Is in [name]. During the active enrollment, paper data will be temporarily kept in a locked cabinet in the study coordinator's office in [name]. The key will be in custody of the PI or study coordinator. Only authorized study staff will have permission to access to paper data.

Electronic data will be stored on the server \\duhsnas-pri\dusom_psych\private\irb\[name]\ wellness pilot and subfolders, maintained by the IT support staff.

Research data will also be collected through REDCap database and Qualtrics. That data will be securely stored on a server hosted by Duke Health Technology Services (DHTS).

Study tracking data (e.g., data on participants' progress through the study, on their status as enrolled/completed/etc) will be stored on Duke General Internal Medicine Divisions' Microsoft SQL Server running on a Windows Server maintained by DHTS. Access to the SQL Server data is managed via Active Directory Groups. Permissions is only granted to documented study personnel authorized to access the data. Access to the Study Tracking application is managed by [name] who built and manages the Study Tracking System.

DEDUCE reports used for identifying eligible patients will be saved on the study server.

The subject payment forms will be stored on the psychiatry server \\duhsnas-pri\dusom_psych\private\Exper Subject-BehMed.

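### Does the recruitment summary have to be split by study condition, given that patients are recruited after their provider is randomised?

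*Combined protocol and SAP*

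**What the plan says.** Section 4 (Design & Procedures) sets the order of events. "Once consented, providers will be randomized to the intervention or comparison condition". Patients with visits booked with those providers are then found, approached and consented: "Participants will be recruited for and enrolled in the study arm that their provider was assigned to". On size, "We will recruit up to 12 patients per provider, for up to 72 total participants", with 60 intended. Section 6 adds that patients who appear eligible from the record search "will be emailed a recruitment letter that is signed by the patient's primary care provider"; study staff then telephone those who do not opt out.

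Section 12 describes the primary outcomes as feasibility and acceptability, mostly descriptive. Item 1 promises "Descriptive data on recruitment rate (number of eligible patients identified and proportion of eligible patients who consent", plus reasons for ineligibility and for declining, and a chi-square comparison by whether a baseline visit was required. It does not mention study condition. Item 5 says 6-month completion rates "will be presented for entire sample and will be presented by study condition and demographics". Item 6 gives descriptive data on program enrolment, sustained use and weight change, "including presenting it by study condition".

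Aim 1 in Section 2 lists provider recruitment, patient recruitment and assessment retention as its feasibility indicators.

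**The concern.** When clusters are randomised first and individuals are recruited afterwards, randomisation does not protect against consent that differs by arm. Here the invitation carries the name of a provider whose arm is already fixed, and the documents do not say that recruiting staff are unaware of it. If patients of intervention providers consented more readily, or were a different kind of patient, the by-condition figures in items 5 and 6 would compare groups that differed at entry.

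A pooled recruitment rate cannot show this. The cap of 12 per provider can hide it in the enrolled counts too, because both arms may fill to the same number from very different pools. Aim 1 asks whether a cluster randomised trial is feasible, so a reader might expect the pilot to describe recruitment by arm. That two later items name study condition and item 1 does not makes the silence look like a decision.

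**Working it through.** **The plan's own figure.** 6 providers × 12 patients = 72, as stated. The intended 60 is 60 / 6 = 10 per provider.

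**What the cap allows.** With six providers allocated 1:1, an arm holds at most 3 × 12 = 36. If 60 enrol, the other arm has at least 60 − 36 = 24, so splits run from 36/24 to 30/30.

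**Can a pooled rate hide a difference?** The documents give no number of eligible patients. Assume 225, with 30 enrolled in each arm. Overall consent is 60 / 225 = 26.7% in every row.

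| Eligible by arm (assumed) | Consent by arm | Difference |
|---|---|---|
| 125 / 100 | 30/125 = 24.0% vs 30/100 = 30.0% | 6.0 points |
| 135 / 90 | 30/135 = 22.2% vs 30/90 = 33.3% | 11.1 points |
| 150 / 75 | 30/150 = 20.0% vs 30/75 = 40.0% | 20.0 points |

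So it can. These splits are invented. They show what is arithmetically possible, not what is likely.

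**How much would a by-arm display tell the reader?** Take p = 60/225 = 0.267, n = 225/2 = 112.5 eligible per arm and m = 225/6 = 37.5 per provider.

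- Half-width = c × √(2p(1 − p)/n × DE), with DE = 1 + (m − 1) × ICC = 1 + 36.5 × ICC.
- √(2 × 0.267 × 0.733 / 112.5) = 0.0590.

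| ICC (assumed) | DE | Normal, c = 1.96 | t on 4 df, c = 2.776 |
|---|---|---|---|
| 0 | 1.000 | 11.6 points | 16.4 points |
| 0.01 | 1.365 | 13.5 points | 19.1 points |
| 0.05 | 2.825 | 19.4 points | 27.5 points |

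The 6.0- and 11.1-point differences lie inside all six half-widths. The 20.0-point difference exceeds five of the six. The half-widths assume equal numbers eligible and a common rate, so they are approximate for the unequal splits above.

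Varying the assumed total, with 60 enrolled and the normal multiplier:

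| Eligible | Pooled rate | Half-width, ICC 0 | Half-width, ICC 0.05 |
|---|---|---|---|
| 120 | 50% | 17.9 points | 25.0 points |
| 200 | 30% | 12.7 points | 20.5 points |
| 300 | 20% | 9.1 points | 16.8 points |

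**Does the silence in item 1 mean exclusion?** Item 3 covers the experience of the medical visit. Section 4 collects this from participants in both arms, yet item 3 names no split by condition either. Mention of arm is uneven across Section 12, as in an outline, so its absence from item 1 is weak evidence that a pooled-only display is intended.

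**Can the counts be recovered?** Arm is fixed by provider. Section 5 requires an upcoming appointment and at least one earlier one with that same provider. The letter is signed by the patient's own provider, so staff must link each candidate to a provider before contact. The cap of 12 also requires a count per provider. Section 14 says "DEDUCE reports used for identifying eligible patients will be saved on the study server" and that study tracking data are stored. Item 1 already requires reasons for ineligibility and decline, so these must be recorded for people who do not enrol.

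**The case for a change.** The strongest case for a change is that Aim 1 concerns a cluster randomised trial in particular. Recruitment after allocation is the feature of that design most likely to make the arms differ at entry, the plan names study condition where it wants that split, and adding it would cost almost nothing. Descriptive counts can inform the next trial even when they are imprecise, and a gap as large as 20 points would probably be noticed.

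Much of this stands. The order of events is as described, item 1 does omit the split, and the counts would be useful to a reader. What does not stand is the step from useful to needed. The mechanism is plausible but not shown: candidates come from a record search on listed criteria, the email goes out from a study address, study staff make the calls, and Section 8 of the concern's chain, the offer described under Study Interventions (Section 9), is the same free programs in both arms. Any differential effect would depend on the letter and the wording of the call, which are not in the documents. With about three providers per arm, an arm difference could not be well separated from differences between providers. A further comparison of consenters with non-consenters would need permission to use record data that the documents do not establish.

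One related point is correct but separate. Aim 1 names provider recruitment and Section 12 lists no summary of it. With at most six providers, the number recruited is a single count that any report will give; only the number approached has to be noted at the time.

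**Conclusion.** No change to the plan follows. This is a gap in a brief descriptive outline that an analyst can be expected to fill sensibly when laying out participant flow by arm.

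Followed exactly as written, item 1 gives a correct overall recruitment rate. The chi-square comparison concerns a separate random assignment of patients and does not depend on a split by condition. Items 5 and 6 remain descriptive, and item 6 already says the study is underpowered for conclusions about program enrolment. The maximum of 72 and the target of 60 are unaffected.

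The loss, if nobody tabulated by arm, would be one descriptive breakdown with a 95% half-width of roughly 12 to 28 points (225 eligible, ICC 0 to 0.05, normal or t on 4 df), or 9 to 25 points across 120 to 300 eligible with the normal multiplier. The eligible totals and ICCs are assumptions. The conclusion that the counts can be recovered rests on stored records identifying each candidate's provider, which the invitation procedure and the per-provider cap both imply but the protocol does not state outright.
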